### PRINCIPAL INVESTIGATOR: [name] Shirley Ryan AbilityLab [name] [contact]

#### **VERSION NUMBER: 7**

#### VERSION DATE: January 8, 2019

#### **OBJECTIVES:**

Aim 1: Determine the capability of an anti-serotonergic agent to reduce hyperexcitability poststroke without compromising voluntary strength.

Aim 2: Assess the efficacy of using a multimodal intervention combining an antimonoaminergicagent with upper extremity training.

Hypothesis: We investigators hypothesize that the group receiving the combined cyproheptadine and active movement therapy will have better outcomes than the groups receiving passive therapy or placebo.

#### BACKGROUD:

Chronic sensorimotor impairment of the upper extremity is prevalent in more than 6 million stroke survivors in the U.S. (Go, et al., 2013), especially in the distal upper extremity (Trombly, 1989). In our studies of the impairment mechanisms of hand motor control after stroke, e.g., (Cruz, et al., 2005; Kamper, et al., 2006; Triandafilou, et al., 2011), we have been struck by two phenomena which arise following the original brain lesion; i) involuntary hyperexcitability of the motor units in certain muscles and ii) the difficulty in producing and controlling voluntary muscle activation. We propose to directly treat both of these phenomena simultaneously in order to improve motor control of the hand and arm. We will reduce motoneuronal hyperexcitability through administration of an anti-serotonergic drug which does not increase weakness, and we will guide the generation of proper muscle activation with a custom device and computer program. We believe that our multimodality treatment approach is innovative in that we combine the use of pharmacological agents with individualized movement therapy in a manner that can be used with patients with poor initial motor control. In separate preliminary studies, we were able to show that a single dose of the agent cyproheptadine could reduce unwanted muscle excitation without decreasing voluntary strength (Seo, et al., 2011) and that active motor training, assisted by an electromyographically (EMG) controlled actuated glove, could lead to statistically significant improvement both in measures of impairment and task performance. In this study, we will combine these approaches to create a novel treatment paradigm for improving motor control of the distal upper extremity after stroke. These techniques are amenable to rapid and widespread integration into the clinic for the arm and hand, and could be applied to the lower extremity as well.

## INCLUSION AND EXCLUSION CRITERIA:

The following groups of individuals will be excluded from this study:

- Adults unable to consent
- Individuals who are not yet adults (infants, children, teenagers)
- Pregnant women
- Prisoners

In this study, we will recruit stroke survivors who:

- are between the ages of 18 to 80;
- have sustained a single, unilateral stroke at least 6 months prior to enrollment;
- have substantial hand impairment as rated at Stage 2 or Stage 3 on the Stage of Hand section of the Chedoke-McMaster Stroke Assessment (Gowland, et al., 1993).

Subjects are excluded if they have:

- excessive pain in the paretic upper limb;
- cerebellar involvement;
- contracture in the paretic upper limb;
- hemispatial neglect (as assessed by the Behavioural Inattention Test (Wilson, et al., 1987));
- apraxia of the paretic upper limb (as assessed by the FABERS battery (Power, et al., 2010));
- rheumatoid arthritis or other orthopaedic impairments restricting finger or wrist movement;
- conditions which necessitate the use of medication that may interfere with neuromuscular function.
- history of seizure disorder
- altered dose of anti-spasticity medication (within 1 month of study start)
- *botulinum toxin injection(s) to the upper extremity (within prior 6 months of study start)*
- contraindicated conditions of the study drug, cyproheptadine (including hypersensitivity to cyproheptadine and other drugs of similar chemical stucture; monoamine oxidase inhbitor (MAOI) therapy, angle-closure glaucoma, stenosing peptic ulcer, symptomatic prostatic hypertropy, bladder, stomach or bowel obstruction, eldery debilitated patients

### STUDY-WIDE NUMBER OF PARTICIPANTS: N/A

### STUDY-WIDE RECRUITMENT METHODS: N/A

### MULTI-SITE RESEARCH: N/A

### STUDY TIMELINES:

After completing a preliminary screening and enrolling in the study by signing the informed consent, each subject will undergo a medical examination with the study doctor to verify suitability for participation. A clinical assessment will be conducted to allow for a stratified group randomization based upon the Fugl-Myer Assessment (FMA) upper extremity score. The subject will then be added to the queue to begin participation.

A subject in the study will be asked to participate for a total of 13 weeks. Training sessions will occur within a 6-week span, starting Week 4. These training sessions will be divided into 3 1-

hour visits a week, for a total of 18 sessions. Additionally, participants will be asked to come to the Arms and Hands Lab for 7 evaluation sessions, each lasting approximately 2 hours. These will take place during the titration phase (baseline and end of weeks 1, 2, and 3), at the midpoint of training (end of week 6), at the end of training (end of week 9), and one month following (end of week 13) (see Fig 1).

[figure not shown]

Figure 1: Timeline for evaluation visits (baseline and end of weeks 1-3, 6, 9 and 13) and treatment therapy sessions (3 visits per week for weeks 4-9). Note that you will also be escorted to the outpatient lab area at the baseline visit and the end of week 3 (during chronic drug dose) to have your blood drawn.

- Anticipated enrollment of participant's completion date: October 2020.
- The estimated date for the investigators to complete this study: October 2022

## STUDY ENDPOINTS:

Primary Outcome Measure:

Change in mean completion time for Graded Wolf Motor Function Test (GWMFT) Secondary Outcome Measure:

Change in grip relaxation time (following a maximum voluntary contraction (MVC)) Time required for muscle electromyographic (EMG) signals to reduce to within 3 SD of pre-MVC EMG activity.

### PROCEDURES INVOLVED:

Study Design:

[figure not shown]
Treatment, Parallel Assignment, Double Blind (Subject, Caregiver, Investigator, Outcomes Assessor), Randomized, Efficacy Study.

Over the course of the study, subjects will participate in a therapy regimen involving either active practice of hand and arm movements or passive stretching of the digits, while concurrently receiving either cyproheptadine or placebo. Thus, the study has two experimental factors: Drug (cyproheptadine hydrochloride/placebo) and rehabilitative movement training (active/passive). Subjects will be randomly divided into four groups, stratified by initial FMA score, consisting of the four combinations of Drug and Training:

- cyproheptadine with active movement training
- placebo with active movement training

- cyproheptadine with passive stretching
- placebo with passive stretching.

Twenty-five subjects in each group will complete the study for a total of 100 participants. The therapists, other research personnel (including the PI), and the subjects will all be blinded as to which agent each subject is taking.

**Fig. 2**. Dosage and evaluation scheduling for the subjects. During the titration period, dosage is increased each week from 8 mg/day toward the target chronic dose of 24 mg/day. The 6 weeks of training will occur once the chronic dose has been established. Arrows indicate evaluation sessions.

As cyproheptadine can have side effects, the dosage is generally titrated over time to the desired chronic daily dose in order to permit accommodation to the drug. This dosing schedule can alleviate the severity of some of the side effects. For this study, both cyproheptadine and the placebo will be titrated in the same manner, beginning at up to 8 mg (up to 4 mg taken 2 times daily) and increasing the next week to up to 16 mg (up to 8 mg taken 2 times daily) and reaching the desired dose level of up to 24 mg per day (up to 8 mg taken 3 times daily) the following week (Fig. 2). If side effects occur at higher doses, but not at lower doses, the subject will be maintained at the highest dose tolerated for the remainder of the treatment phase. Participants will maintain this daily dosage for 6 weeks, during which time training will be performed. After completion of the training period, dosage levels will be reduced back to zero over a two-week period. The drug dosage may be reduced from the target level as recommended by the study doctor.

[figure not shown]
The hospital pharmacy will dispense the allotment of the study drug to research staff at each change in dosage over the course of the study (5 dispenses). All pills will be encapsulated by the Research Pharmacist so that both cyproheptadine and placebo will be identical in appearance and weight. Only the Research Pharmacist and study Statistician will have the key identifying which drug each subject was given. In this manner all other study personnel, including the PI, and the subjects will remain blinded as to group membership until the study is complete, or the revealing of this information is deemed medically necessary. Each week during the titration period, the subject will come to the Arms and Hands lab to receive his/her weekly allotment of pills from study staff. Examination by the study doctor will occur at baseline, midpoint, and at the end of the study. To monitor type and severity of potential adverse side effects of the medications, the study doctor or a study team member will complete a checklist for each subject weekly. All subjects, even those in the placebo group, will be given this checklist. Adverse side effects will be rated as "none", "moderate", or "severe" based on subject report. If a subject feels unable to

continue the study due to any side effects, she may end her study participation at that time. Transportation can be arranged to convey subjects to and from the Shirley Ryan AbilityLab during this period in order to preclude the need for subjects to drive when they may be experiencing dizziness or somnolence from the medication. Weekly pill counts will be performed to gauge subject compliance with taking the medication. Participants will receive the subsequent allotment of pills at each dosage change.

Once the chronic dosage is attained, therapeutic training will begin for all subjects. The sensorimotor therapy, consisting of 18 one-hour sessions held over 6 weeks, will focus on the impaired upper extremity, particularly the hand.

[figure not shown]

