electrodes (Bagnoli) from EDC and FDS. Subject strength will also be assessed, by having subjects perform maximum voluntary MCP flexion and extension in the same testing jig while the servomotor provides resistance. The EMG data recorded during these isometric contractions will be used to quantify coactivation. Finally, FDS relaxation time will be determined by having the subject create maximal grip force in the jig and then relax upon hearing the termination of an auditory tone, as we have done previously. Both upper extremities may be tested in a subset of participants in order to determine the impact of cyproheptadine on the non-paretic (ipsilesional) side.

Clinical assessments will be performed at the baseline, pretreatment (week 3), mid, post and follow up evaluation sessions by the study research therapist and study team. This battery of assessments includes the GWMFT, FMA, Chedoke McMaster Stroke Assessment – Stage of Hand (CMSA-H), grip and pinch strengths, the Modified Modified Ashworth Scale (MMAS), the Jebsen Hand Function Test, the Nine-Hole Peg Test, the Box and Blocks Test (BBT), and the Semmes Weinstein Monofilament Touch test.

In addition to these neuromechanical measurements, subjects will be evaluated in terms of sleepiness, depression, and weight gain. These are side effects that could dissuade use of the medication. The Epworth Sleepiness Scale (ESS) will be given to subjects at each testing session (Johns, 1991). This instrument consists of a self-assessment of the propensity to doze (ordinal scale, 0-3) during each of 8 activities of daily living (e.g., sitting and talking to someone). We will use the Beck Depression Inventory-II (BDI-II) for assessing depression in our subjects. The BDI-II is a self-report of 21 items rated on an ordinal scale from 0-3 (Beck, et al., 1996). The BDI-II, a revised version of the Beck Depression Inventory (Beck, et al., 1961), was developed to remove possible bias for older adults from the original instrument. Additionally, subjects will be weighed each week to track fluctuations in weight.

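### The masking claim names no factor, but only the drug is masked: training arm is open to subjects and trainers, and no assessor masking to training is specified

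*Protocol*

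**What the plan says.** Under PROCEDURES INVOLVED, the Protocol's design line reads "Double Blind (Subject, Caregiver, Investigator, Outcomes Assessor": four roles and no factor. The same section sets out a 2 x 2 design with the factors "Drug (cyproheptadine hydrochloride/placebo) and rehabilitative movement training (active/passive", and forms four groups from their combinations, with 25 completers in each.

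The section makes three further statements about blinding:

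- Therapists, other research personnel (the PI included) and subjects "will all be blinded as to which agent each subject is taking".
- The mechanism is that "both cyproheptadine and placebo will be identical in appearance and weight", and that "Only the Research Pharmacist and study Statistician will have the key identifying which drug each subject was given".
- It then concludes that all other personnel and "the subjects will remain blinded as to group membership until the study is complete", unless disclosure is medically necessary.

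The Outcome Measures section has the clinical battery, which includes the GWMFT, performed at baseline, week 3, midpoint, end of training and follow-up "by the study research therapist and study team". STUDY ENDPOINTS makes change in mean GWMFT completion time the primary outcome. The hypothesis under OBJECTIVES is that the combined cyproheptadine and active-training group "will have better outcomes than the groups receiving passive therapy or placebo".

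**The concern.** A masking statement tells readers how far they can trust a comparison. In a two-factor trial it has to be made for each factor, because the two can differ completely. Here the label and the group-membership sentence cover both factors, while the procedures cover one.

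The primary outcome is a timed performance test given by study staff, so encouragement, prompting and the call on when a task is finished all pass through a person. If that person knows the training arm and expects active training to do better, the active-versus-passive contrast can be biased. Knowledge of the arm may also affect a subject's own effort. A report that repeats the design line would describe that contrast as double blind with a masked assessor, and the Protocol as written would not support the description.

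**Working it through.** The plan gives no figure for masking. The only power figure in the documents is for the Drug comparison in Aim 1 (SAP: effect size 0.22, 80% power, α 0.05, 50 per Drug group), and this point does not depend on it. For completeness, treat it as a between-subject effect over four sessions with 1 and 98 degrees of freedom and λ = f²·N·m/(1+(m−1)ρ). With N = 100, m = 4 and an assumed ρ of 0.5, λ = 0.0484 × 400/2.5 = 7.74 and power is 0.787, close to the stated 80%. The SAP does not give ρ: power is 0.885 at ρ = 0.3 and 0.657 at ρ = 0.8.

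**Step 1: masking by factor and role.**

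| Role | Drug | Training |
|---|---|---|
| Subject | Masked: identical capsules | Cannot be masked: the subject either does EMG-driven practice and games or has the digits moved by the glove |
| Person delivering sessions | Masked: no access to the key | Cannot be masked: runs the session |
| Outcome assessor | Masked: no access to the key | Nothing specified |
| PI and other personnel | Masked: no access to the key | Nothing specified |

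The contents of the two kinds of training come from the Active Movement Therapy and Passive Stretching sections. They are different activities that anyone in the room can tell apart.

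**Step 2: the group-membership sentence.** The groups are defined by drug and training together. Someone who knows the training arm has already narrowed four groups to two. The sentence can be true of drug assignment but not of group membership as the Protocol defines it.

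**Step 3: which comparisons are exposed.** The hypothesis sets the combined group against three others.

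| Comparator of cyproheptadine + active | Crosses training arms? | Labelled masking supported? |
|---|---|---|
| Placebo + active | No | Yes |
| Cyproheptadine + passive | Yes | No |
| Placebo + passive | Yes | No |

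The Training main effect is exposed in the same way. Aim 1 is not: the SAP analyses Drug by Session from pre-administration to week 3, and training starts in week 4. The baseline and week 3 GWMFT also precede any training session, so the exposed assessments are those at weeks 6, 9 and 13.

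**Step 4: which outcomes.** The GWMFT and the rest of the clinical battery depend on the person giving them. The secondary outcome, grip relaxation time, comes from an EMG threshold and leaves less room for rater judgement, though subject effort can still affect it.

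**Step 5: sensitivity, under assumptions.** Suppose there is no true training effect, the assessor shifts every subject's result by δ SD in favour of active training, and the arms are compared by a two-sided 5% two-sample t-test. Both the shift and the test are assumptions: the SAP text available refers to an Aim 2 analysis but does not contain it. Each training arm has 2 × 25 = 50 completers. The non-centrality is δ·√(n/2): 5δ for n = 50 (df 98) and 3.54δ for a single pair of arms with n = 25 (df 48).

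| Assumed shift δ | False-positive rate, 50 v 50 | False-positive rate, 25 v 25 |
|---|---|---|
| 0.1 SD | 7.9% | 6.4% |
| 0.2 SD | 16.8% | 10.7% |
| 0.3 SD | 31.8% | 18.0% |

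**The case against.** The strongest reply is that the Protocol already limits the blind. The body text speaks of the agent, and the capsules and key concern the drug. On that view the design line is shorthand needing one clarifying phrase. This is largely fair: no training blind is described that then fails. But the group-membership sentence goes beyond shorthand, and the assessor's position on training is left open either way.

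A reader might infer that the therapist who trains a subject also scores that subject. The documents do not say so. Outcome Measures names a research therapist and team without saying who delivers training, and therapists are elsewhere mentioned in the plural, which is compatible with separate people. What can be said is that neither separation nor masking to training is specified.

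A reader might also infer that half of the factorial trial is compromised. That goes too far, because drug contrasts within a training arm and all of Aim 1 keep their masking.

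The passive arm deserves credit. It matches laboratory and device exposure in order to address a placebo effect, and subjects who know what they are doing need not know which arm is the comparator. The consent material is not in the text available, so what they are told cannot be judged. This softens the concern about subject expectation but does nothing to mask an assessor.

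Finally, the shift sizes have no source in the documents and are applied uniformly to a timed test. They show what a bias of that size would do, not that one is likely.

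**Conclusion.** The point stands in limited form. The design line and the group-membership sentence claim more masking than the procedures provide. For Training, the claim cannot be true of subjects or those who deliver sessions, and it is unsupported for assessors. What is affected is the Training main effect and the contrasts across training arms, including two of the three comparisons in the stated hypothesis, chiefly on the primary GWMFT and the other staff-administered clinical measures.

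That much follows from the text alone. The false-positive rates of about 8%, 17% and 32% rest on assumed shifts and an assumed test. They are not evidence of bias and should not set the weight given to the point. It merits a change because the primary outcome is staff-administered, the hypothesis depends on cross-training contrasts, and the correction is cheap.

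**What to change.** 1. State masking separately by factor: double blind for Drug; Training open to subjects and trainers. In the sentence on the drug key, replace group membership with drug assignment.
2. State that, within the existing team, the person who scores a subject's GWMFT and clinical battery does not deliver that subject's training and is not told the training arm. If staffing does not allow this, remove the outcomes assessor from the masking claim for Training.
3. Report contrasts across training arms as not subject-masked.

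Items 1 and 3 cost only wording. Item 2 adds a scheduling constraint. The documents do not give staffing numbers, and SETTING places training and hand evaluation in one laboratory, so an assessor may still see a subject being trained. The rule would reduce knowledge of the arm without guaranteeing masking, which is why the alternative of withdrawing the assessor claim is offered.

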Title: Altering Activation Patterns Post-stroke **NCT:** NCT02418949 **Date:** 6/4/2014

Analysis: Spasticity will be quantified using the MCP angular position and torque data from the trials of imposed MCP rotation [27, 66-68]. Namely, the nominally passive torque curve (recorded during the 10°/s trial) will be subtracted from the total torque curve (recorded during the 300°/s). Mean reflex torque will then be computed from the resulting signal by averaging across a 300-ms period beginning at the end of stretch. The EMG data, normalized by the values recorded during maximum contraction, will be used to confirm that a reflex occurred. The FDS signal must surpass a threshold of 5% of maximal contraction for classification as a spastic stretch reflex and subsequent evaluation. Coactivation during voluntary tasks will be computed from the ratio of normalized EDC/FDS for flexion and FDS/EDC for extension. Values closer to 0 indicate less coactivation. Relaxation time will be estimated as the elapsed time from cessation of the auditory tone to the FDS signal dropping below a threshold level equal to three standard deviations of the resting signal [34]. Active isometric flexion and extension torque will be found by subtracting the initial, passive torque from the peak torque recorded during the respective trials.

Statistical analyses will be employed to assess the effect of cyproheptadine on these outcome measures. We will perform repeated measures analysis of variance (rmANOVA) with the between-subject factor Drug (cyproheptadine, placebo) and the within-subject factor evaluation Session (pre-administration, week 1, week 2, week 3 - see Fig. 1). To test the first hypothesis, addressing efficacy in reducing hyperexcitability, the measures spastic reflex, FDS relaxation time, and coactivation ratio will be used as dependent variables in a MANOVA. Should evidence of a significant effect appear, i.e., a Wilk's lambda value < 0.05, we will perform subsequent post-hoc ANOVAs to test the effects on individual dependent variables. To examine the second hypothesis, regarding loss of strength, separate rmANOVAs will be conducted for extension and flexion strength. Similarly, as we wish to minimize Type II errors for these potentially negative outcomes, separate rmANOVAs will be run for ESS and BDI-II without correction. Normality of the residuals will be tested for these parametric tests and non-parametric tests will be run if normality assumptions are violated.

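### The study statistician holds each subject's drug key during the trial, although no task described in the supplied documents needs it: an avoidable risk that is cheap to remove

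*Protocol*

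**What the plan says.** Three parts of the Protocol section PROCEDURES INVOLVED bear on this.

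- The study design line lists the blinded roles: "Double Blind (Subject, Caregiver, Investigator, Outcomes Assessor), Randomized, Efficacy Study". A data analyst or statistician is not among them.
- The design description adds: "The therapists, other research personnel (including the PI), and the subjects will all be blinded as to which agent each subject is taking".
- The dispensing text gives custody of the key: "Only the Research Pharmacist and study Statistician will have the key identifying which drug each subject was given". It continues that "all other study personnel, including the PI, and the subjects will remain blinded as to group membership until the study is complete", or until disclosure is medically necessary.

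On allocation, the same section says: "Subjects will be randomly divided into four groups, stratified by initial FMA score". It does not say who prepares the list.

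The SAP (Analysis) writes in the first person plural: "We will perform repeated measures analysis of variance (rmANOVA) with the between-subject factor Drug (cyproheptadine, placebo" and a within-subject Session factor. Its rule for departures from the model is: "Normality of the residuals will be tested for these parametric tests and non-parametric tests will be run if normality assumptions are violated". It assigns none of this work to a named role.

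**The concern.** A pharmacist who prepares the capsules and may have to break the code needs the link from subject to drug. An analyst usually does not need it until the analysis is settled. When the analyst has it earlier, each judgement made while cleaning data or choosing a method can be influenced, without intent, by knowing which subjects received the active drug. A reader of the final report cannot tell whether that happened.

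The risk is small where every step is written down in advance. It is larger where steps remain open, and the supplied SAP leaves some open. The drug comparison is also the one that the placebo and the identical capsules are meant to protect, so leaving its analyst unmasked without a stated reason gives away part of that protection.

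**Working it through.** The SAP and protocol give no figure on this point, so there is none to reproduce. The check sets the relevant texts side by side.

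**1. Who knows, and when.** The dispensing text names two key holders, the Research Pharmacist and the study Statistician. It then keeps all *other* personnel blinded until completion. Together these sentences mean that both holders have subject-level drug information during the trial. This is stated, not inferred.

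**2. Does a described task need it?** The custody sentence is the only mention of a statistician in either document. The possible reasons are:

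| Possible reason | What the documents say |
|---|---|
| Interim analysis or sample-size re-estimation | None described |
| Safety review by drug | Given to a medical/data monitor (Protocol, provisions to monitor the data); no report by drug from the statistician described |
| Medically necessary code break | The pharmacist also holds the key |
| Preparing the FMA-stratified list | Not assigned to anyone; can be done with coded arms |
| Aim 2 analysis, including the primary GWMFT outcome | The SAP points to an Aim 2 analysis section that is not in the supplied text |

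No described task requires the key. The last row limits that statement to the supplied text.

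**3. Which analysis steps are fixed, and which are open?**

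- Fixed: the rmANOVA factors; the MANOVA on three hyperexcitability measures with follow-up ANOVAs; the reflex rule (FDS above 5% of maximum); the 300-ms averaging window; the three-standard-deviation relaxation threshold.
- Open: which normality test is used and at what criterion; which non-parametric test replaces the two-factor repeated-measures model. The supplied SAP text is also silent on missing values.

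**4. Who makes the open choices?** The SAP says only *we*. The study Statistician is the one statistical role named, so it is reasonable to infer that this person makes or advises on them. It remains an inference.

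**5. Is there any other safeguard?** No text in either document calls for masked group codes, or for the open choices to be settled before the key is available to the person making them.

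**Result.** Steps 1, 2 and 5 establish early access without a described need and without a safeguard. Steps 3 and 4 show that the access could matter, on condition that the statistician runs the analysis.

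**The case against.** **The strongest case against** is that the harm is conditional and narrow. The SAP does not say that the statistician analyses the data; if blinded laboratory staff do, the mechanism fails. Someone must create the stratified list, which is an ordinary reason for a statistician to hold it. The main Aim 1 models are specified, and outcome assessors, therapists and subjects stay blinded. All of this stands and keeps the severity low. It does not supply a need for the key, because a list with coded arms serves the same purpose.

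A reader might infer four stronger things that the documents do not support.

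- *That unblinding inflates the type I error by a calculable amount.* In a simulated null trial of 50 v 50, reporting whichever of a t-test or rank test is significant gives about 6% for normal data and about 7% for right-skewed data (lognormal, log-SD 0.7 to 1.0, assumed). But a two-sided p-value is identical when the group labels are swapped, so an analyst with A/B labels could make the same choice. That inflation comes from free choice between tests, not from holding the key. Nor is free choice what the SAP describes: its trigger is the residuals. Following that rule, with Shapiro-Wilk at 0.05 assumed, gives 5.0% (normal), 5.0% (log-SD 0.7) and 4.8% (log-SD 1.0).
- *That the statistician can decide which reflexes count.* The SAP fixes this with the 5% FDS threshold, and nothing assigns the classification to the statistician.
- *That the plan contradicts its own double-blind label.* The listed roles do not include the analyst. The broader sentence on other research personnel sits awkwardly with the custody sentence, but the latter is specific and makes an explicit exception.
- *That allocation may leak through the statistician to the study team.* The protocol says all others remain blinded, and nothing suggests otherwise.

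**Conclusion.** The point holds as a cheap improvement of low severity. The protocol expressly gives the statistician the subject-level drug key during the trial, and no task in the supplied documents needs it. If the statistician also runs the analysis, the unnamed normality criterion, the unnamed fallback test and any data-handling decisions could be settled with knowledge of who takes cyproheptadine.

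This is a risk of directional bias that could be avoided. It is not evidence that bias occurred, and no error rate can be attached to it from the documents. The conclusion rests on two assumptions: that the statistician does the analysis, and that the Aim 2 analysis text, which was not supplied, contains no task requiring the key.

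**What to change.** Amend the custody sentence in the protocol's procedures section, and add a short paragraph to the SAP:

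1. Only the Research Pharmacist holds the link from arm code to drug.
2. The statistician may prepare the FMA-stratified list with coded drug arms, and receives data labelled A/B.
3. The SAP names the normality rule and the fallback test. These and the analysis program are final before any outcome is compared by coded arm.
4. The code is opened only after database lock.

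Item 3 is needed as well as the coding, because labels alone do not prevent a choice between tests after both results are seen.

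**Cost.** A sentence in the protocol, a paragraph in the SAP and a coded list; no extra subjects or visits. There is a small downside. One fewer person holds the key, and the pharmacist would have to supply any data by drug that the monitor requests. If the statistician does have a task that needs the key, the protocol should state it and assign the analysis to someone who works from the coded data.
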